12.1.2 Secondary Objectives / Outcome Measures

- Best disease response, whether complete remission (CR), complete remission with incomplete marrow recovery (Cri) or partial remission (PR), to treatment in a) the initial phase of the study at or before the 6 month assessment and b) the Extension Study at or before the 9 month assessment. Independent decisions will be made for each study (initial and extension)., assessed according to the IWCLL Criteria (revised 2008) (Appendix 1). The dynamics of response will be assessed both in terms of the change in absolute levels of CLL in the blood and marrow as well as the changes in the proliferating compartment and changes in chemokine receptor.
- 1 and 2 year progression free survival for relapsed/refractory and treatment naïve patients defined as time from date of registration to date of progression (per the modified 2008 IWCLL criteria) or death from any cause. Alive patients who are progression free will be censored at their date of last follow-up.
- 1 and 5 year overall survival for relapsed/refractory and treatment naïve patients is defined as the time from date of registration to the date of death from any cause.
- Toxicity of ibrutinib and obinutuzumab
- CLL cell levels as a percentage of total leucocytes in the bone marrow (BM) and absolute counts in the peripheral blood (PB).
- The proportion of patients with >5%, 0.5-5%, <0.5% CLL cells in cell cycle (expressing Ki67) in the peripheral blood and bone marrow in a) the initial phase of the study at or before the 6 month assessment and b) the Extension Study at or before the 9 month assessment
- Change in the expression levels of CD10, CD103, CD11c, CD185, CD196, CD20, CD200, CD22, CD23, CD25, CD27, CD305, CD31, CD38, CD39, CD43, CD49d, CD5, CD79b, CD81, CD95, IgD, IgG, or IgM on CLL cells relative to baseline by more than 50% and at least 500 arbitrary units in median fluorescence intensity.

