2.2 Outcome Measures

Primary outcome measures

Proportion of patients achieving MRD-negative remission by IWCLL criteria (depletion of CLL below 0.01% in the peripheral blood and bone marrow) in a) the initial phase of the study at or before the 6 month assessment and b) the Extension Study at or before the 9 month assessment. Independent decisions will be made for each study (initial and extension).

Secondary outcome measures:

- Best disease response to treatment: Complete Remission (CR); Complete Remission with incomplete marrow recovery (Cri) or Partial Remission (PR) with leucocytosis, assessed according to the IWCLL Response Criteria (revised 2008) (Appendix 1) in a) the initial phase of the study at or before the 6 month assessment and b) the Extension Study at or before the 9 month assessment. Independent decisions will be made for each study (initial and extension) 1 and 2 year progression free survival for relapsed/refractory and treatment naïve patients defined as time from date of registration to date of progression (per the 2008 IWCLL criteria) or death from any cause
- 1 and 5 year overall survival for relapsed/refractory and treatment naïve patients, defined as the time from date of registration to the date of death from any cause
- Toxicity of ibrutinib and obinutuzumab
- CLL cell levels as a percentage of total leucocytes in the bone marrow (BM) and absolute counts in the peripheral blood (PB)
- The proportion of patients with $>5\%$, $0.5-5\%$, $<0.5\%$ CLL cells in cell cycle (expressing Ki67) in the peripheral blood and bone marrow in a) the initial phase of the study at or before the 6 month assessment and b) the Extension Study at or before the 9 month assessment
- Change in the expression levels of CD10, CD103, CD11c, CD185, CD196, CD20, CD200, CD22, CD23, CD25, CD27, CD305, CD31, CD38, CD39, CD43, CD49d, CD5, CD79b, CD81, CD95, IgD, IgG, or IgM on CLL cells relative to baseline by more than 50% and at least 500 arbitrary units in median fluorescence intensity

Exploratory outcome measures:

- Change in phosphoprotein expression (including Akt, Syk, MAPK, ERK and Btk) at screening in CLL cells stimulated with immunoglobulin in the presence and absence of *in vitro* ibrutinib and during/after treatment in CLL cells stimulated with immunoglobulin measured as fluorescence intensity in arbitrary units relative to unstimulated cells/control

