3. ICICLLE TRIAL DESIGN

IcICLLe Study (initial phase)

A feasibility study to investigate i) the mechanism of action of ibrutinib and ii) the biological response to ibrutinib in two separate cohorts of patients; (A) treatment naïve and (B)i relapsed/refractory CLL.

There will be 20 patients in each cohort; therefore a total of 40 patients will initially be recruited.. All patients will receive continuous oral therapy with ibrutinib (420 mg OD) from registration until disease progression.

We will test the patterns of response to ibrutinib in both the treatment naïve and the relapsed/refractory patient cohorts.

IcICLLe Extension Study

The *IcICLLe extension study* will investigate if ibrutinib combined with obinutuzumab can increase the number of patients achieving MRD negativity in peripheral blood and bone marrow.

Two cohorts of patients will be evaluated; cohort (B)ii ibrutinib naïve relapsed/refractory CLL patients, and cohort (B)iii patients initially enrolled on the IcICLLe trial as relapsed/refractory patients and treated with at least 6 months of ibrutinib therapy (i.e. previously in cohort (B)i).

Please note that treatment naïve patients enrolled on IcICLLe in the initial phase—cohort (A)—will not be eligible to take part in the IcICLLe Extension Study and thus will continue with ibrutinib monotherapy.

In the IcICLLe extension study, ibrutinib and obinutuzumab will be administered in combination. Ibrutinib will be given as continuous oral therapy (420 mg OD) from registration until disease progression. **The ibrutinib naïve cohort in the IcICLLe extension study should receive ibrutinib 24 hours before the obinutuzumab (Day 0) to help reduce potential infusion reactions.** Obinutuzumab will be given intravenously at a dose of 1000 mg on days 1, 8, and 15 of cycle 1 and on day 1 of cycles 2- 6 (see section 7.1 for further information of obinutuzumab scheduling)

We will test the patterns of response to ibrutinib and obinutuzumab in both the ibrutinib-naïve and ibrutinib-treated relapsed/refractory patient cohorts.

By studying this and deriving the mechanism of action in both treatment arms we hope to ascertain the most appropriate drugs to combine with ibrutinib and inform how this might be done. This will help to define if this is an appropriate drug to use in combination and/or to take forward into randomised Phase II/III trials of ibrutinib in CLL.

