4. ELIGIBILITY

4.1 Inclusion Criteria

Cohort (A): Treatment naïve (initial phase only – 20 patients)

- Progressive Stage A, Stage B or Stage C CLL (Appendix 7)
- CLL requiring therapy by the IWCLL criteria (Appendix 1)
- ECOG performance status (PS) of 0, 1, or 2 (Appendix 6)
- Life expectancy of at least 6 months
- Age ≥ 18
- Prepared to undergo the stipulated investigations within the trial (including bone marrow examinations)
- Able to give informed consent
- Adequate hepatic function, defined as serum aspartate transaminase (AST) or alanine transaminase (ALT) $< 2.5 \times \text{ULN}$, and total bilirubin $\leq 1.5 \times \text{ULN}$ unless due to Gilbert's syndrome
- Adequate renal function, defined as estimated creatinine clearance $\geq 30 \text{ ml/min}$ using the Cockcroft-Gault equation

Cohort (B)i and (B)ii: Relapsed/refractory (initial phase – 20 patients, extension phase between 20-40 patients)

- B-CLL requiring therapy according to the IWCLL guidelines
 - The leukaemia cells should co-express CD19, CD5, and CD23 and each clone should have restricted to expression of either kappa or lambda immunoglobulin light chains.
 - The levels of surface immunoglobulin, CD20, and CD79b should be low. If there is atypically strong surface immunoglobulin, CD20, or CD79b expression, or other atypical features, it may not be possible to perform the MRD monitoring required to evaluate the primary endpoint.¹²
- Refractory/relapsed CLL defined as any of the following:
 - Failure to achieve a response (CR or PR by IWCLL Criteria) to a purine analogue alone or in combination with chemotherapy, or:
 - Relapse within 6 months of responding to a purine analogue alone or in combination with chemotherapy, or:
 - Relapse at any time after fludarabine, cyclophosphamide and rituximab (FCR) or bendamustine plus rituximab, or:
 - Patients with CLL with deletion of chromosome 17p who have failed at least one previous therapy.
- ECOG PS of 0, 1, or 2 (see Appendix 6)
- Life expectancy of at least 6 months
- Prepared to undergo the stipulated investigations within the trial (including bone marrow examinations)
- Age ≥ 18
- Able to give informed consent
- Ability to comply with study protocol procedures
- Adequate hepatic function, defined as serum aspartate transaminase (AST) or alanine transaminase (ALT) $< 2.5 \times \text{ULN}$, and total bilirubin $\leq 1.5 \times \text{ULN}$ unless due to Gilbert's syndrome

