12.1.3 Exploratory outcome measures

- Change in phosphoprotein expression (including Akt, Syk, MAPK, ERK and Btk) at screening in CLL cells stimulated with immunoglobulin in the presence and absence of *in vitro* ibrutinib and during/after treatment in CLL cells stimulated with immunoglobulin measured as fluorescence intensity in arbitrary units relative to unstimulated cells/control.
- Assessment of the mechanism of response and resistance to ibrutinib in patients with lack of or failure to maintain a response or disease progression compared to those patients with good responses (mutation analysis of key BCR pathway genes, gene expression profiling and epigenetic modifications)
- Response correlated with secondary prognostic markers (such as FISH, IGHV, CD38/CD49d expression)
- Change in the expression levels of BCL2, IRF4, ZAP70, CD62L, CD184, CD80, CD40, CD11a, CD54, CD154, CCR7, CD24, CD86 on CLL cells relative to baseline by more than 50% and at least 500 arbitrary units in median fluorescence intensity.
- The absolute numbers and proportions of CD4+ and CD8+ T-cell subsets with respect to expression of CD27, CD62L, CD45RA, CCR4 and CXCR3.
- Assessment of MRD levels using novel technologies including high throughput sequencing

Data on outcome measures will be collected as stipulated in the protocol of this feasibility study to confirm the mechanism of action of ibrutinib/obinutuzumab. Results from this trial will then inform the design of a randomised phase II trial using response as the primary outcome measure to determine whether ibrutinib/obinutuzumab shows sufficient evidence of activity in these cohorts of patients.

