12.2 Analysis of Outcome Measures

12.2.1 IcICLE (initial phase)

Statistical analysis in this study, will be based on descriptive statistics only.

The primary endpoint is the dichotomous variable, MRD Negativity. The precise specification for determining whether a patient is MRD-negative is detailed in section 7.2.3

The number and proportion of patients in each response category will be reported with 95% confidence interval and presented as a proportion of the total number of patients recruited to this study.

- The number and proportion of patients experiencing any grade haematological and non-haematological toxicities will be reported as a proportion of the number of patients recruited.
- Survival estimates will be calculated using the method of Kaplan and Meier, and point estimates reported with 95% CIs.
- The number and proportion of patients with abnormalities in chromosome 11 or 17, or with an unmutated IGHV gene will be reported.

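### The marker outcomes count only changes above 50% that are also at least 500 units, so a marker starting below 500 units can be recorded as rising but not as falling

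*Protocol*

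**What the plan says.** Section 12.1.2 lists 24 surface markers as a secondary outcome and counts a change in expression "on CLL cells relative to baseline by more than 50% and at least 500 arbitrary units in median fluorescence intensity". Section 2.2 states the same criterion ("IgG, or IgM on CLL cells relative to baseline by more than 50% and at least 500 arbitrary units in median fluorescence intensity"), as does the synopsis. Section 12.1.3 applies it to 13 further exploratory markers. The percentage and the absolute condition are joined by a plain conjunction, so both must be met. None of these places gives a separate rule for markers with a low baseline.

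Two neighbouring laboratory outcomes carry no cut. Phosphoprotein expression is "measured as fluorescence intensity in arbitrary units relative to unstimulated cells/control", and CLL cell levels are given as marrow percentages and blood counts. Section 12.1.2 also mentions, under the dynamics of response, "as well as the changes in the proliferating compartment and changes in chemokine receptor", but gives no scale and does not refer to the marker list.

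For the initial phase, section 12.2.1 says: "Statistical analysis in this study, will be based on descriptive statistics only". On cohort size, section 3 says: "There will be 20 patients in each cohort; therefore a total of 40 patients will initially be recruited". For cohorts (B)i and (B)ii, section 4.1 adds: "The levels of surface immunoglobulin, CD20, and CD79b should be low". CD20, CD79b, IgD, IgG and IgM are all on the secondary list.

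**The concern.** Median fluorescence is continuous, and each patient is measured before and during treatment. Reducing that to whether two thresholds are both passed discards most of the information. Here it also does so unevenly, because the absolute condition limits falls and rises differently. A fall is bounded by the starting value and a rise is not. The criterion therefore favours rises over falls at low baselines, and bright markers over dim ones.

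This bears on a stated purpose of the initial phase, which is to study the mechanism of action of, and biological response to, ibrutinib. If the outcome is reported as defined, a marker that was lost, or that moved consistently but moderately in every patient, could be described as unchanged. In a descriptive study such a misdescription is the main harm to guard against.

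**Working it through.** The protocol states no sample size, power or error rate for this outcome, so there is no figure of its own to reproduce. The check applies the rule literally.

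**Inputs.** The rule is from 12.1.2; 20 patients per cohort is from section 3. Write B for baseline and F for follow-up intensity, with F ≥ 0 (an assumption; the protocol does not say whether background is subtracted).

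**Rule.** A change is recorded if |F − B| / B > 0.5 and |F − B| ≥ 500. The absolute change needed is therefore the larger of 0.5 × B (to be exceeded) and 500 (to be reached).

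**Falls.** The largest possible fall is B − 0 = B. If B < 500, then B − F ≤ B < 500 and the second condition fails. Enumerating every whole-number baseline from 1 to 499 with every lower follow-up value gives no recorded case. From 450 to 0 is a fall of 450, which is not recorded. From 450 to 1,000 is a rise of 550, or 122%, which is recorded.

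**Minimum recorded change as a percentage of baseline** (500 / B below 1,000 units, 50% from there up):

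| Baseline | Fall needed | Rise needed |
|---|---|---|
| 100 | impossible | 500% |
| 200 | impossible | 250% |
| 400 | impossible | 125% |
| 500 | 100% | 100% |
| 600 | 83.3% | 83.3% |
| 800 | 62.5% | 62.5% |
| 1,000 and above | more than 50% | more than 50% |

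The same proportional fall is treated differently by starting level. An 80% fall is recorded at 625 units (0.8 × 625 = 500) but not at 624 (0.8 × 624 = 499.2).

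**Consistent moderate shifts.** A uniform shift of 30%, 40% or exactly 50%, up or down, in all 20 patients is recorded in 0 of 20 at baselines of 400, 800, 2,000 and 10,000. The percentage condition alone ensures this at any baseline.

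**Illustration with assumed inputs.** None of the following is in the protocol: lognormal baseline with log SD 0.5, true median fall of 40%, SD of the log change between 0.1 and 0.4. The share of patients recorded as changed is:

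- median baseline 300: 0% to 0.8%
- median baseline 800: 1.2% to 15.9%
- median baseline 2,000 to 5,000: 3.1% to 33.4%

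The ranges show how strongly the result depends on the baseline level and on between-patient spread, neither of which the protocol gives.

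**The case against.** **A floor has a purpose.** An absolute minimum joined to a percentage plausibly screens out noise near background. As an illustration, assume a median baseline of 300 units, no true change, biological log SD 0.2 and measurement noise of SD 100 to 150 units on both readings. A fall of more than 50% then appears in about 12% to 19% of unchanged patients, against about 0.1% to 0.9% with the 500-unit condition added. This stands. It is a reason to keep the criterion as a flag and not to waive the 500-unit condition for decreases. It is not a reason to make the flag the outcome.

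**The baseline levels are unknown.** A reader might infer from the entry criterion that CD20, CD79b and surface immunoglobulin will in fact start below 500 units. The text does not support that. It gives no units, low need not mean below 500, and it covers only cohorts (B)i and (B)ii.

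**No test is planned.** A reader might also express the loss as power, setting a test on log ratios against a test on flagged patients. The protocol plans neither for these markers, and the initial phase is descriptive, so such figures would compare procedures from outside the plan.

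**Continuous values may be reported anyway.** The wording does not forbid this, and a statistical analysis plan that is not at hand may provide for it. The protocol itself nevertheless fixes the outcome at the double threshold.

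**Log ratios fail at zero.** A change from 450 to 0 has no finite log ratio. This stands, and the fix has to deal with it.

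**Conclusion.** The concern holds as a weakness in how the outcome is defined. Given non-negative intensities, three consequences follow from the rule alone: decreases cannot be recorded below 500 units; the fall required between 500 and 1,000 units runs from 100% down to 50%; and a shift of 50% or less in every patient reads as no change at any baseline. If background-subtracted values below zero were used, the bar would be severe but not absolute: a baseline of 400 would have to reach −100 or lower.

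The practical size cannot be determined from the protocol, because it does not state how many markers or patients start below 500 units. Importance is moderate to low. These are secondary and exploratory descriptive measures. The primary MRD endpoint, the activity decision rule in 12.2.2 and the toxicity guidelines in 12.6 do not depend on them.

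**What to change.** In 12.1.2 and 12.1.3, and to match in 2.2 and the synopsis, define the marker outcome as the continuous within-patient change from baseline in median fluorescence intensity at each scheduled visit. Report it descriptively per cohort, for example as the median fold change with a 95% CI, or as a geometric mean ratio with values floored at assay background so that zero readings are handled. Keep the present double criterion unchanged as a supplementary flag, and state next to it that it cannot register decreases from baselines below 500 units.

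The cost is wording and some extra tabulation. The intensities are already to be measured, so no samples, visits or patients are added. There are two downsides. Ratios for very dim markers will be noisier, which their intervals should show. With 24 + 13 = 37 markers the results must be read as description, not confirmation.

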12.1.3 Exploratory outcome measures

- Change in phosphoprotein expression (including Akt, Syk, MAPK, ERK and Btk) at screening in CLL cells stimulated with immunoglobulin in the presence and absence of *in vitro* ibrutinib and during/after treatment in CLL cells stimulated with immunoglobulin measured as fluorescence intensity in arbitrary units relative to unstimulated cells/control.
- Assessment of the mechanism of response and resistance to ibrutinib in patients with lack of or failure to maintain a response or disease progression compared to those patients with good responses (mutation analysis of key BCR pathway genes, gene expression profiling and epigenetic modifications)
- Response correlated with secondary prognostic markers (such as FISH, IGHV, CD38/CD49d expression)
- Change in the expression levels of BCL2, IRF4, ZAP70, CD62L, CD184, CD80, CD40, CD11a, CD54, CD154, CCR7, CD24, CD86 on CLL cells relative to baseline by more than 50% and at least 500 arbitrary units in median fluorescence intensity.
- The absolute numbers and proportions of CD4+ and CD8+ T-cell subsets with respect to expression of CD27, CD62L, CD45RA, CCR4 and CXCR3.
- Assessment of MRD levels using novel technologies including high throughput sequencing

Data on outcome measures will be collected as stipulated in the protocol of this feasibility study to confirm the mechanism of action of ibrutinib/obinutuzumab. Results from this trial will then inform the design of a randomised phase II trial using response as the primary outcome measure to determine whether ibrutinib/obinutuzumab shows sufficient evidence of activity in these cohorts of patients.

12.2 Analysis of Outcome Measures

12.2.1 IcICLE (initial phase)

Statistical analysis in this study, will be based on descriptive statistics only.

The primary endpoint is the dichotomous variable, MRD Negativity. The precise specification for determining whether a patient is MRD-negative is detailed in section 7.2.3

The number and proportion of patients in each response category will be reported with 95% confidence interval and presented as a proportion of the total number of patients recruited to this study.

- The number and proportion of patients experiencing any grade haematological and non-haematological toxicities will be reported as a proportion of the number of patients recruited.
- Survival estimates will be calculated using the method of Kaplan and Meier, and point estimates reported with 95% CIs.
- The number and proportion of patients with abnormalities in chromosome 11 or 17, or with an unmutated IGHV gene will be reported.

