5. SCREENING AND CONSENT

5.1 Informed Consent

It is the responsibility of the Investigator or delegate, to obtain written informed consent for each patient prior to performing any trial related procedure. A Patient Information Sheet is provided to facilitate this process. Investigators must ensure that they adequately explain the aim, trial treatment, anticipated benefits and potential hazards of taking part in the trial to the patient. The Investigator should also stress that the patient is completely free to refuse to take part or withdraw from the trial at any time. The patient should be given ample time (e.g. 24 hours) to read the Patient Information Sheet and to discuss their participation with others outside of the site research team. The patient must be given an opportunity to ask questions which should be answered to their satisfaction. The right of the patient to refuse to participate in the trial without giving a reason must be respected.

If the patient expresses an interest in participating in the trial they should be asked to sign and date the latest version of the Informed Consent Form. The Investigator or designate must then sign and date the form. A copy of the Informed Consent Form should be given to the patient, a copy should be filed in the hospital notes, and the original placed in the Investigator Site File (ISF). Once the patient is entered into the trial the patient's trial number should be entered on the Informed Consent Form maintained in the ISF. In addition, if the patient has given explicit consent a copy of the signed Informed Consent Form must be sent in the post to the Trials Office for review.

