5.3.2 Assessments 2 weeks before the treatment start date

These assessments are to be performed **within the two weeks** prior to registration and following consent

- **Clinical assessment of lymph node disease:**
 - The size of the largest lymph nodes in each nodal area (cervical, axillary and inguinal) should be measured in centimetres in 2-dimensions
- **Clinical assessment of liver and spleen:**
 - If palpable, size of liver and spleen below costal margin should be measured.
- **Pregnancy test** (in women of child bearing potential **within 2 weeks** prior to starting treatment)
- **Samples to send for central analysis** (see section 7.3 for details of how to do this):
 - 0.5 - 2 mL first-pull bone marrow aspirate
The first draw of bone marrow aspirate should be put in EDTA and is used for MRD flow cytometry (the less the marrow is diluted with blood the more accurate the assessment of involvement by CLL).
 - Bone marrow trephine biopsy (directly in formalin)
 - 4 x 5 mL peripheral blood in EDTA

Please note:

1. Samples sent for central analysis must be sent on Monday or Tuesday two weeks prior to the provisional treatment start date agreed with the IcICLLe trial office.
2. Confirmation by the HMDS that this two week peripheral blood sample is viable will be required before the patient starts treatment. If this sample is not viable, an additional peripheral blood sample will be requested and confirmed to be viable before the patient starts ibrutinib treatment.
3. IcICLLe Extension Study patients who are rolling over from IcICLLe and have undergone bone marrow examination within 6 months of starting the Extension Study are NOT required to have bone marrow examinations at screening

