6. TRIAL ENTRY

Patients must be registered with the Cancer Research UK Clinical Trials Unit (CRCTU) at the University of Birmingham. The patient's eligibility will be confirmed at registration. If eligible for the study, the patient will be allocated a Patient Trial Number (TNO). The registration line will be open during office hours (9-5pm, Monday-Friday).

Registration line: [name]
Monday - Friday, 9-5pm

IcICLLe Extension Study

Relapsed/refractory patients who have received ibrutinib on IcICLLe who wish to join the extension study need to consent and (re-)register for the extension study. Ibrutinib naïve patients will need to consent and be registered for the IcICLLe extension study. **All patients entering the extension study will receive a new trial number (TNO).**

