8.1.4 Reporting period

Details of all AEs (except those listed above) will be documented and reported from the date of commencement of protocol defined treatment until 30 days after the administration of the last treatment (refer to Treatment Schedule A and B).

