12.3 Planned Sub Group Analyses

The data from the initial and Extension phases of the study will be analysed separately.

In the initial phase, the two-cohorts, A and B(i), will be analysed separately. The immunoglobulin mutation status (mutated [$>98\%$ similarity to germ-line] versus unmutated [$>98\%$ similarity to germ-line]) will be analysed separately as will patients with 17p deleted and 11q deleted CLL.

In the extension phase the same analysis applies to the two cohorts B(ii) and B(iii)..

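### Initial-phase toxicity is reported per patient recruited, but adverse events are collected only once treatment starts, so any registered patient who is never dosed lowers the rate

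*Protocol*

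**What the plan says.** Section 12.2.1 sets out a descriptive analysis of the initial phase and names a denominator for two outcomes. Response categories are "presented as a proportion of the total number of patients recruited to this study". Haematological and non-haematological "toxicities will be reported as a proportion of the number of patients recruited". The two outcomes therefore share one denominator.

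Section 8.1.4 fixes the window for adverse event data: events are documented and reported "from the date of commencement of protocol defined treatment until 30 days after the administration of the last treatment".

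Trial entry and first dose are separate steps. Under section 6 the patient enters at registration, when eligibility is confirmed and a trial number is given. Section 5.3.2 adds a condition on dosing: "Confirmation by the HMDS that this two week peripheral blood sample is viable will be required before the patient starts treatment". Section 3 states the intention that "All patients will receive continuous oral therapy with ibrutinib (420 mg OD) from registration until disease progression", but gives no rule for a patient who does not start. The protocol defines no treated-patient safety population and no replacement rule for patients who are never dosed.

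On cohorts, section 12.3 states: "In the initial phase, the two-cohorts, A and B(i), will be analysed separately". Section 3 sets 20 patients per cohort, 40 in total.

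**The concern.** A denominator of everyone recruited suits response, because a patient who never starts treatment counts as a non-responder and the estimate errs against the drug. For toxicity the same choice works the other way. Toxicity requires exposure, and no adverse event data are collected before exposure, so an undosed patient is in effect counted as free of toxicity. The error has one possible direction, and it makes ibrutinib look safer.

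Toxicity is a named secondary outcome, and section 1.2.2 gives low toxicity as a particular attraction for relapsed/refractory patients. An understated rate is therefore the less welcome kind of error, even if it is small.

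**Working it through.** **Plan's own figures.** The protocol attaches no number to this denominator. Its nearest toxicity figures are the initial-phase stopping guidelines in section 12.6.1. An exact two-stage binomial calculation gives 95.1% and 77.1% for treatment-naïve patients (stated 95% and 77%), and 93.1% and 75.7% for relapsed/refractory patients (stated 93% and 75%). These agree to within a percentage point and are not in question. They are built on patient counts, and the percentage in 12.2.1 does not feed them.

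**Inputs.**
- N = 20 per cohort, 40 overall (section 3), with the cohorts analysed separately (section 12.3).
- u = number registered but never dosed. The protocol gives no value; 0 to 2 per cohort is an assumption.
- p = true rate of a toxicity among treated patients. The values 10% and 30% are used for illustration.

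**Dilution.** Toxicities arise only among the N − u treated patients, but the count is divided by N:

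reported rate = p × (N − u) / N

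| N | u | Factor | p = 30% reported as | p = 10% reported as |
|---|---|---|---|---|
| 20 | 0 | 20/20 = 1.00 | 30.0% | 10.0% |
| 20 | 1 | 19/20 = 0.95 | 28.5% | 9.5% |
| 20 | 2 | 18/20 = 0.90 | 27.0% | 9.0% |
| 40 | 1 | 39/40 = 0.975 | 29.25% | 9.75% |
| 40 | 2 | 38/40 = 0.95 | 28.5% | 9.5% |

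Within a cohort, each undosed patient takes 1/20 = 5% off the rate in relative terms. Over all 40 patients it is 1/40 = 2.5%.

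**Same count, two denominators.** Suppose 6 patients in a cohort of 20 have a given toxicity. The 95% intervals below are Clopper-Pearson intervals added here to give scale; section 12.2.1 asks only for the number and proportion for toxicity, with no interval.

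| Undosed | Patients recruited | Patients treated | Difference |
|---|---|---|---|
| 0 | 6/20 = 30.0% (11.9 to 54.3) | 6/20 = 30.0% (11.9 to 54.3) | 0 |
| 1 | 6/20 = 30.0% | 6/19 = 31.6% (12.6 to 56.6) | 1.6 points |
| 2 | 6/20 = 30.0% | 6/18 = 33.3% (13.3 to 59.0) | 3.3 points |

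The interval for 6/20 is 54.3 − 11.9 = 42.4 points wide, so the shift is small next to sampling error. Unlike sampling error, it always goes the same way.

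**With treated patients as the denominator.** The factor becomes (N − u)/(N − u) = 1, and the true rate is recovered whatever u is.

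**The case against.** The strongest reply is that the problem may never occur. Ibrutinib is meant to start at registration, screening precedes registration, eligibility is confirmed at registration, and a patient with an active infection cannot be registered until it has resolved. Section 12.5.1 expects high compliance and little loss to follow-up. The sample-viability check in section 5.3.2 carries its own remedy, a repeat sample, so it may delay the first dose but does not by itself exclude a patient. The consent statement in section 5.1 that "the patient is completely free to refuse to take part or withdraw from the trial at any time" is standard wording and shows only that withdrawal before day 1 is allowed.

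It can also be said that the analysis is descriptive, that the count is reported beside the percentage so a reader who knows how many were treated can recalculate, and that patients recruited is at least a transparent choice in a single-treatment feasibility study.

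Most of this stands as an argument about size: the number of undosed patients is probably small and may be zero. It does not remove the point. Starting at registration is an intention, and the expectations in section 12.5.1 do not concern patients who never start. Nor is the matter left to the SAP. The protocol names the denominator, so an SAP that used treated patients would contradict it, and one that followed it would carry the bias.

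**Conclusion.** The concern holds, as a minor point. Sections 12.2.1 and 8.1.4 together place never-dosed patients in the denominator of a rate whose numerator they cannot enter, so the reported initial-phase toxicity can be biased only downwards. With 1 or 2 undosed patients in a cohort of 20, a true 30% is understated by 1.5 or 3.0 points and a true 10% by 0.5 or 1.0 point. This rests on the assumed number of undosed patients; with none, there is no effect. The mismatch itself is certain from the text. Whether it will alter any reported figure in this trial is not known. No decision rule and no efficacy conclusion depends on it.

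**What to change.** In section 12.2.1, change the toxicity denominator from patients recruited to patients who received at least one dose of trial treatment, and report how many were registered but not treated. Leave patients recruited as the denominator for response.

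The cost is one phrase. Toxicity and response tables may then carry different denominators, which a table footnote can explain, and toxicity percentages may be slightly higher. If every registered patient was dosed, no number changes. If the initial-phase analysis has already been done, the same correction can be made in the report.
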